**Step 2: Combination of events:**

Overlapping/consecutive events are defined as events of the same participant with the same preferred term which have at least 1 day overlap or for which the start date of an event is 1 day after the end date of the preceding event. Overlapping/consecutive events may be combined into one AE or not, according to the following rules:

1. If overlapping/consecutive events start in one of the following phases/periods - Screening or Follow-up (defined as non-active periods) - followed by an AE in – a Post-dose period (defined as active period) - they are allocated to their respective phases/periods and are considered as separate events.
2. In case overlapping/consecutive events start within a single period, they are considered as one and the same AE. The individual events which contribute to this AE are retained as individual records in the ADaM database but are assigned the same onset, period, and total duration. All related attributes to the AE/phase/period should also be consistent with the new event.
3. In case overlapping/consecutive events start in both an active period followed by one or more consecutive non-active periods, they are allocated to the active period only and are considered as one and the same AE. The individual events which contribute to this AE are retained as individual records in the ADaM database but are assigned the same onset, treatment period, and total duration. All related attributes to the AE/phase/period should also be consistent with the new event.
4. In case an active period is followed by another active period, and the overlapping/consecutive events start in both periods, they are allocated to their respective period and are considered as separate AEs. In case overlapping/consecutive events start in non-consecutive periods (regardless of active or non-active), they are allocated to their respective period and are considered as separate AEs.
5. In case a non-active period is followed by another non-active period, and the overlapping/consecutive events start in both periods, they are allocated to the first period and they are considered as one and the same AE. The individual events which contribute to this AE are retained as individual records in the ADaM database but are assigned the same onset, period, and total duration. All related attributes to the AE/phase/period should also be consistent with the new event.

Remarks:

1. Events can only be combined into one and the same AE if their start and stop dates are known.
2. In case the completely missing end date is imputed (for period allocation), this date is also considered as a complete date.
3. Time is not considered when determining overlap of events.

**5.6.1.4. Missing Data**

Missing data will not be imputed. Participants who do not report an event will be considered as participants without an event. An AE with a missing severity or relationship will be considered as an AE reported, but will be considered as not reported for the severity or relationship. For example,

an AE with missing severity will be considered as an AE reported for the analysis of any grade but will be considered as not reported for the analysis of at least grade 3.

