## 4. POPULATIONS (ANALYSIS SETS) FOR ANALYSIS

Population	Description
Full Analysis Set (FAS)	The full analysis set will include all participants with at least one vaccination documented. All safety and participant information analyses will be based on the FAS.

Population	Description
Per-protocol Immunogenicity (PPI)	
The PPI population will include all randomized and vaccinated participants for whom immunogenicity data are available excluding samples taken on or after the date when a participant experiences a major protocol deviation expected to impact the immunogenicity outcomes.
 
In addition, samples obtained after missed doses or samples obtained after natural infection (if applicable) will be excluded from the analysis.
 
 
For participants who experience a natural influenza infection (based on RT-PCR, or other sources), samples collected within 7 days prior to and after the natural infection (e.g. start of reporting of ILI symptoms) will not be considered in the assessment of the immunogenicity of the selected regimen.
 
If a participant misses one or more active dose(s) of the selected regimen but continues the planned visit schedule, samples after the missed active dose(s) will not be considered.
 
 
The analysis of all secondary and exploratory immunogenicity endpoints will be based on the PPI set.
 
A sensitivity analysis may be performed to assess the impact of suspected sub-clinical influenza infection on immunogenicity. Suspected sub-clinical influenza infection will be defined at a given time point if a participant has a fold-increase from baseline for the full-length H5 ELISA four times greater than the fold-increase from baseline for the H5 VNA. Samples collected after suspected sub-clinical influenza infection will be excluded from this analysis.
 
Depending on the number of samples excluded, an exploratory analysis might be performed, including the excluded samples. To visualize excluded samples, participant profiles from several assays might be repeated, indicating the excluded samples.

Vaccine assignment will follow the as-treated principle (participant will be presented according to received vaccine group).

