**Table 1: Phase Definitions**

Phase	Phase #	Period	Period #	Interval	
				From	To
Screening	1			Date and time of signing the informed consent form a	One minute prior to start of Post-dose 1 period
Regimen	2	Post-dose 1	1	Date and time of first vaccination	Minimum of: a) 23:59 at the date of last contact (for early discontinuation) b) 23:59 at the date of database cut-off date in case of interim c) 23:59 on 28 days after the first vaccination (23:59 of day of vaccination + 28 days) d) One minute prior to Post-dose 2
Follow-up 1	3	Follow-up 1		One minute after post-Dose 1 period end	Minimum of: a) 23:59 at the date of last contact (for early discontinuation) b) 23:59 at the date of database cut-off date in case of interim c) One minute prior to Post-Dose 2
Regimen	2	Post-dose 2	2	Date and time of second vaccination	Minimum of: a) 23:59 at the date of last contact (for early discontinuation) b) 23:59 at the date of database cut-off date in case of interim c) 23:59 on Day 28 after the second vaccination (23:59 of day of vaccination + 28 days)
Follow-up 2	4	Follow-up 2		One minute after Post-dose 2 period end	Minimum of: a) 23:59 at the date of last contact b) 23:59 at the date of database cut-off date in case of interim

a In case an earlier date is available (e.g., for lab or vital signs), then use the very first date to include all data.

Note: participants who did not receive a second vaccination will not have a Post-dose 2 or Follow-up 2 period.

The periods/phases will be used primarily for allocation of adverse events to various time periods during the study. Adverse events will be summarized for each of the active periods, 'Post-dose 1' and 'Post-dose 2', as well as Post-dose 1 and Post-dose 2 Combined, which is referred to as

‘Regimen’. Additionally, for SAEs and AEs leading to discontinuation of study vaccine tables, an ‘Entire study’ period will be defined. ‘Entire study’ covers the time window from vaccination 1 up to and including the end of the study for each participant.

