## **5.6. Other Safety Analyses**

Safety analyses will be performed on the FAS. Continuous variables will be summarized using the following statistics, as appropriate: number of observations, arithmetic mean (mean), 95% CI for the mean (if applicable, large studies), standard deviation (SD), standard error (SE), median, quartiles (Q1 and Q3), minimum, and maximum. Frequencies and percentages (one decimal place) will be generated for categorical variables. No formal comparisons between groups will be provided.

Two types of safety tables will be shown. In the by regimen layout, safety data will be analyzed by study intervention regimens as designed per protocol. In case of multiple vaccinations, data will be presented by phase as well as over the entire regimen. The denominator for the percentages is the number of participants in the considered population and phase for a certain regimen (incidence per 100 participants/phase). In the second, by vaccine layout, only limited safety data will be presented by the different vaccines used in the study but by considering every vaccination administered as a separate safety episode. The denominator for the percentages is the number of vaccinations administered of a certain vaccine (rate per 100 vaccinations of a particular vaccine). DPS will define which tables will be provided by vaccine layout.

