## **5.6.1. Adverse Events**

### **5.6.1.1. Definitions**

Solicited AEs are used to assess the reactogenicity of the study vaccine and are predefined local events (pain/tenderness, erythema, and swelling at the injection site) and systemic events (fatigue, headache, nausea, myalgia, and fever) for which the participant is specifically questioned, and which are noted by participants in their reactogenicity diary. Unsolicited AEs are all AEs for which the participant is not specifically questioned.

Solicited AEs shown in the tables are extracted from the investigator assessment pages (CE) of the CRF. For unsolicited AEs, only the AEs within the 28-day period following each vaccination will be presented in the safety tables. SAEs will be captured and tabulated in the outputs covering the whole study period. All other collected unsolicited adverse events will be presented through listings.

The verbatim terms used in the eCRF by investigators to identify AEs will be coded using the Medical Dictionary for Regulatory Activities (MedDRA).

Solicited administration site symptoms will be considered as related to the study vaccine.

The severity of the AEs will be classified as grade 1 to 4. Solicited events that are graded less than grade 1, are not considered as AE. In case no grades are available, the grading of the solicited events will occur according to the grading list in Appendix 6.

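### A vaccinated participant with no solicited follow-up after the day of vaccination is counted as a non-reactor, so if any such participants exist the tabulated solicited-AE rate is the lowest one compatible with the data

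*SAP*

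**What the plan says.** SAP 5.3.1 lists solicited local and systemic AEs for 7 days after each vaccination as a primary endpoint. Three rules then fix how the rate is formed.

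- **Non-reporters.** SAP 5.6.1.4: "Participants who do not report an event will be considered as participants without an event". The sentence stands under 5.6.1, which defines both solicited and unsolicited AEs, and it does not separate them.
- **Denominator.** SAP 5.6, by-regimen layout: "The denominator for the percentages is the number of participants in the considered population and phase for a certain regimen". By-vaccine layout: "The denominator for the percentages is the number of vaccinations administered of a certain vaccine".
- **Population.** SAP 4: "The full analysis set will include all participants with at least one vaccination documented". No diary or assessment is required.

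On the source of the events, SAP 5.6.1.1 says: "Solicited AEs shown in the tables are extracted from the investigator assessment pages (CE) of the CRF". Each post-dose period is tabulated, "as well as Post-dose 1 and Post-dose 2 Combined, which is referred to as" Regimen (SAP 5.1.2). Someone who never received dose 2 is not a problem here: "participants who did not receive a second vaccination will not have a Post-dose 2 or Follow-up 2 period".

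The SAP defines no denominator based on solicited follow-up. Its disposition and exposure outputs (5.2, 5.2.1) do not ask how many participants have solicited data for a dose.

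**The concern.** For unsolicited AEs and SAEs, treating no report as no event is the usual convention, because nobody is asked about a fixed list. Solicited AEs are different. Participants are asked about named symptoms every day, and the severity tables in Protocol Appendix 4 define a Grade 0. Being followed without a reaction and not being followed are therefore distinguishable states, and the SAP rule merges them. The same paragraph says that missing data are not imputed, yet for a participant without follow-up the rule acts as an imputation of no reaction.

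At stake is the accuracy of the descriptive reactogenicity rates, which are the primary result and one input to regimen selection (Protocol 9.5, SAP 5.8). Counts by visit would show a missed Day 8 or Day 64 visit. They would not show whether solicited data exist, because a missed diary review moves to the next visit (Protocol 8).

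**Working it through.** **The plan's own figure.** Protocol 9.2 states that no reactions among 25 participants gives 95% confidence that the true rate is below 11.3%, and below 2.0% for 150. The exact one-sided bound is 1 − 0.05^(1/n). For n = 25 it is 11.29% and for n = 150 it is 1.98%, so both figures reproduce. They are right for 25 and 150 participants who were actually followed. With 24 or 23 followed, the same formula gives 11.7% or 12.2%.

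**Inputs.** Group sizes come from Protocol Table 1: 25 per active group, and 10 + 10 = 20 for pooled placebo. The documents give neither a reaction rate nor a number without follow-up, so the values of x and m below are assumptions for illustration.

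**Definitions, for one dose and one solicited event.**
- N = participants vaccinated.
- x = participants with a recorded reaction.
- m = participants with no solicited data after the day of vaccination and no reaction recorded at the 30-minute observation.

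**Formulas.**
- Tabulated rate = x/N.
- Rate among those followed = x/(N − m), when no reaction was seen only at the 30-minute observation.
- Range for all N = x/N to (x + m)/N, with width m/N.

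| N | m | x | Tabulated | Among those followed | Range for all N |
|---|---|---|---|---|---|
| 25 | 1 | 14 | 56.0% | 58.3% | 56.0–60.0% |
| 25 | 2 | 14 | 56.0% | 60.9% | 56.0–64.0% |
| 25 | 1 | 7 | 28.0% | 29.2% | 28.0–32.0% |
| 25 | 2 | 7 | 28.0% | 30.4% | 28.0–36.0% |
| 20 | 1 | 6 | 30.0% | 31.6% | 30.0–35.0% |

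**Direction.** x/N is the lower end of the range for every x and m, and it never exceeds x/(N − m).

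**Size per participant.** The largest effect is 1/25 = 4 points in an active group and 1/20 = 5 points in pooled placebo. If missing follow-up is unrelated to reactions, the expected shortfall is (m/N) × the true rate. For one of 25 that is 0.04 × 60% = 2.4 points, or 0.04 × 30% = 1.2 points.

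**Unequal follow-up.** Take two groups of 25 with a true rate of 60%. If one group is complete and the other lacks follow-up at random in 2, the expected tabulated rates are 60% and 60% × 23/25 = 55.2%.

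**Why the FAS rate should stay.** Suppose one of 25 has a reaction at the 30-minute observation and no later data, and 13 of the other 24 react. The FAS rate is 14/25 = 56.0%. The rate among those followed is 13/24 = 54.2%, because the documented reaction has dropped out.

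**The case against.** The strongest reply is that the affected group is small by design and may be empty.

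- Site staff document any solicited event after at least 30 minutes of observation (Protocol 1.3.1 footnote j, 8.3.2).
- Every participant is contacted 3 to 5 days after each vaccination visit to check diary completion (1.3.1 footnote b).
- A missed diary review moves to the next visit.
- An early exit within 7 days of vaccination includes solicited recording.

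This stands. It rules out the tempting reading that a participant without a diary has no solicited data at all: the first half hour is covered, and the gap is in later follow-up. It does not say how a participant with that gap is counted, and the SAP rule does.

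A second reply is that safety is descriptive, since "No formal comparisons between groups will be provided", and that the shift is small against the precision. The exact 95% interval for 14/25 is 34.9–75.6%, against a shift of 2.3 points with one participant missing. This also stands and limits the importance of the point. But the shift is systematic and its direction is known, whereas the interval describes sampling error.

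A third reply is that Protocol 9.3 and 9.4.2 put all safety analyses on the FAS and include all reported AEs, so replacing the denominator would depart from the protocol. That is correct, and the main rate should stay as it is.

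Finally, the Data Presentation Specifications were not available and might already contain a count row. They also decide which tables use the by-vaccine layout, so no figure is offered for that layout. The SAP text as written asks for no such count.

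**Conclusion.** The point holds conditionally. Under SAP 5.6.1.4 and 5.6, each vaccinated participant without solicited data after the day of vaccination, and without a reaction seen on site, lowers the tabulated rate by up to 4 points in a group of 25 or 5 points in pooled placebo. The loss is zero if none exist or none of them reacted, and the rule cannot raise the rate. How many such participants there are is unknown from the documents.

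A reader might go further in three ways that the documents do not support.

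- That reactogenicity in this trial is understated: no missingness figure is given, and the safeguards point to few cases or none.
- That the 11.3% planning bound is wrong: it is correct for 25 participants followed.
- That the SAP contradicts itself because it has other missing-data rules. The Flu-iiQ rule in 5.5 concerns an averaged item score. The laboratory and vital-signs rule in 5.6.2 concerns an abnormality that was observed when the baseline is missing. Neither deals with an outcome that was not observed.

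This is a cheap improvement in reporting and does not threaten the trial's conclusions.

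**What to change.** 1. Keep the FAS rate as the main analysis, as the protocol requires. State that it includes any reaction recorded only at the 30-minute observation.
2. In SAP 5.6.1.4, let no report = no event stand as the only treatment for unsolicited AEs and SAEs, but not for solicited AEs.
3. For solicited AEs, show by group and dose the number of vaccinated participants with diary data or an investigator solicited assessment after the day of vaccination. Also show the number with a partial diary, meaning fewer than the 8 scheduled days (day of vaccination plus 7).
4. Beside the FAS rate, give the rate among participants with such data. Decide inclusion by whether an assessment exists, never by its result.
5. For the combined Regimen period, show how many participants have such data after only one of the doses they received.
6. Record the addition in SAP Appendix 2.

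The cost is some SAP and table-specification wording, count rows, and one supplementary rate per solicited-AE table. No new data collection is needed. The supplementary rate overstates reactions if participants who do not return react less than those who do, which is why both rates are shown. A short, event-free diary still counts as event-free; the partial-diary row discloses this but does not remove it. If everyone was followed, the two rates coincide and the report can say so.

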## 2. STATISTICAL HYPOTHESES

No formal statistical hypothesis on safety is to be tested. The study will evaluate whether INFLUENZA G1 mHA, with or without Al(OH)3 adjuvant, is safe, well tolerated, and immunogenic in healthy adults aged  $\geq 18$  to  $\leq 45$  years.

Safety data will be analyzed descriptively per vaccine group (placebo from Cohort 1 and 2 will be combined), with special attention to SAEs, Grade 3/4 AEs, and AEs leading to discontinuation of study vaccine.

No formal hypothesis on immunogenicity will be tested. Immunogenicity data will be analyzed descriptively per study group. Descriptive statistics (geometric mean and 95% CI, or median and quartile range [Q1-Q3], as appropriate) will be calculated for continuous immunological parameters at all time points and for changes from baseline.

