## **5.3. Primary Endpoint(s) Analysis**

### **5.3.1. Definition of Endpoint(s)**

Section 3 of the CTP provides AE definitions associated with primary safety endpoints. The primary endpoints to assess safety are:

- Occurrence, severity, duration, and relationship to study vaccine of solicited local and systemic AEs for 7 days after each vaccination.
- Occurrence, severity, duration, and relationship to study vaccine of unsolicited AEs for 28 days after each vaccination.
- Occurrence and relationship to study vaccine of SAEs from first vaccination to the end of the study.

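### For unsolicited AEs, and for the relationship of solicited systemic AEs, the SAP's missing-attribute rule makes the tabulated Grade 3+ and related rates the minimum that the blank fields allow

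*SAP*

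**What the plan says.** SAP 5.6.1.4 opens with "Missing data will not be imputed". It then covers an AE that was reported but has no severity or no relationship. The event counts as an AE, but for the missing attribute it "will be considered as not reported for the severity or relationship". The SAP's own example is an AE with no severity, which enters the any-grade analysis but "will be considered as not reported for the analysis of at least grade 3".

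SAP 5.6 fixes the denominator of the by-regimen tables: "The denominator for the percentages is the number of participants in the considered population and phase for a certain regimen". A blank attribute does not reduce it.

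Both attributes belong to the primary endpoints. SAP 5.3.1 lists "Occurrence, severity, duration, and relationship to study vaccine of unsolicited AEs for 28 days after each vaccination", with a matching item for solicited AEs, and SAP section 2 promises descriptive analysis "with special attention to SAEs, Grade 3/4 AEs".

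SAP 5.6.1.1 takes part of the solicited data out of the rule's reach. On severity: "In case no grades are available, the grading of the solicited events will occur according to the grading list in Appendix 6". On relationship: "Solicited administration site symptoms will be considered as related to the study vaccine". Protocol Appendix 4 (10.4) says the same about injection-site relatedness and derives the grades of erythema, swelling and fever from measurements.

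**The concern.** The rule applies to events known to have happened. Removing such an event from a numerator while its participant stays in the denominator can lower the Grade 3+ or related percentage and can never raise it.

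Neighbouring SAP rules close gaps the other way:

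- In 5.6.1.3, an AE with no start date at all is placed in the first post-dose period unless its end date precedes that period.
- In 5.6.2, a laboratory or vital-sign abnormality with no baseline is counted as emerging.
- In 5.6.2, a laboratory value that falls in a gap of the grading scale takes the worse neighbouring grade.

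The SAP gives no reason for treating missing AE severity and relationship differently. It also asks for neither a count of missing attributes nor a worst-case analysis; its sensitivity analyses concern immunogenicity. At stake are the Grade 3+ and related rates of a first-in-human vaccine, which are part of the safety results used to choose a regimen (protocol 9.5, SAP 5.8).

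**Working it through.** **1. Where the rule can act** (SAP 5.3.3, 5.6.1.1 and 5.6.1.4; protocol 10.4)

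| Event class | Missing severity | Missing relationship |
|---|---|---|
| Solicited injection-site | Graded from the list or the measurement | Related by rule; no effect |
| Solicited systemic | Graded from the list, or from temperature for fever | Leaves the related and Grade 3+ related counts |
| Unsolicited | Leaves the Grade 3+ and Grade 3+ related counts | Leaves the related and Grade 3+ related counts |

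For a solicited AE, the severity part acts only if no grade can be derived.

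**2. Direction.** Let n be the participants in the group, x those with a recorded qualifying event, and m those whose only candidate event has the blank attribute. Depending on the true values of the blanks, the rate lies between x/n and (x + m)/n. The SAP reports x/n, the lower end.

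**3. The plan's own figures.** Protocol 9.2 gives upper 95% limits of 11.3% for 0/25 and 2.0% for 0/150. The exact one-sided limit for zero events is 1 − 0.05^(1/n):

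- n = 25: 1 − 0.05^(1/25) = 11.29%
- n = 150: 1 − 0.05^(1/150) = 1.98%

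Both match. The two-sided version, with 0.025 in place of 0.05, gives 13.7% and 2.4% and does not match, so the protocol's limits are one-sided.

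**4. Size, as an illustration.** The number of blanks is not in the documents. Assume x = 0 and m from 0 to 3, with every blank resolved as qualifying. The upper limit is the exact one-sided 95% binomial (Clopper-Pearson) limit, the p that solves P(X ≤ m | n, p) = 0.05. For m = 1 and n = 25 this is (1 − p)^25 + 25p(1 − p)^24 = 0.05, so p = 17.6%.

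| m | m/25 | Upper limit | m/150 | Upper limit |
|---|---|---|---|---|
| 0 | 0% | 11.3% | 0% | 2.0% |
| 1 | 4.0% | 17.6% | 0.7% | 3.1% |
| 2 | 8.0% | 23.1% | 1.3% | 4.1% |
| 3 | 12.0% | 28.2% | 2.0% | 5.1% |

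The m = 0 row is what the SAP would tabulate in every case.

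**The case against.** **Blanks should be rare.** Protocol 10.4 requires the investigator to record relationship and all AEs to be graded. Protocol 10.3 has the sponsor review the eCRF for completeness and raise queries. Related Grade 3+ AEs go to the sponsor within 24 hours (8.3.1), and the medical officer examines all Grade 3+ cases (6.8). This stands. It limits the expected size but does not change the direction, and few blanks make the correction nearly free.

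**The analysis is descriptive.** SAP 5.3.3 lists counts and percentages, without confidence limits for Grade 3+ or related rates. This stands: the limits above use the protocol's sample-size yardstick to show scale and are not a planned output.

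**Counting a blank as related is a form of imputation.** Protocol 10.4 also ties relatedness to evidence of a causal link. The fix is therefore a tabulation convention and should be labelled as one. The SAP already uses such a convention for injection-site events.

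Three stronger readings are tempting, and the documents do not support them:

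- *All Grade 3+ and related rates in the trial are the lowest possible.* Injection-site relatedness and derivable solicited grades lie outside the rule.
- *The SAP's safety rules lean generally in the vaccine's favour.* The rules cited above for missing start dates, missing baselines and grading gaps push counts up, and a partial date can place one AE in several periods.
- *The comparison between regimens is distorted, or the reader has no means of seeing the blanks.* The same rule applies to every group, and site staff are blinded. The table shells sit in the separate Data Presentation Specifications, which are not among the documents reviewed. One can say only that the SAP does not require a count.

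**Conclusion.** The point holds for unsolicited AEs (severity and relationship) and for solicited systemic AEs (relationship). There the tabulated Grade 3+ and related rates are minima over the possible values of the missing attribute. The SAP does not formally recode such an event as mild or unrelated, but the effect on those numerators is the same.

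The actual size cannot be calculated. The illustration of 4 percentage points per affected participant in a group of 25, and 0.7 in the pooled 150, assumes the planned group sizes, no other qualifying event in that participant, and a blank whose true value qualifies. This is an inexpensive correction to components of the primary endpoints and does not threaten the validity of the trial.

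**What to change.** In SAP 5.6.1.4:

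1. Count an unsolicited or solicited systemic AE with missing relationship as related in the related tables. State this as an exception to the no-imputation sentence, and label it in the tables as a convention.
2. Footnote the unsolicited Grade 3+ and Grade 3+ related tables with the number of AEs missing severity, by group, and with a worst-case count that includes them. A footnote suits better than an extra row in a by-grade table, because SAP 5.3.3 lists a by-grade table only for solicited AEs, whose missing grades are already to be filled from the grading list.
3. Leave the any-grade count unchanged.

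The cost is a short change to 5.6.1.4 and footnotes on tables already planned. The related figures and the worst-case Grade 3+ figures may look slightly less favourable. If there are no blanks, every figure stays the same and the footnotes read zero.
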